5.4 Inclusion/Exclusion Criteria

Our study population will be comprised of Veterans from the primary care (PC) clinics of three VA medical centers: 1) VA Boston Healthcare System; 2)

Corporal Michael J. Crescenz VA Medical Center (Philadelphia); and 3) Ralph H. Johnson VA Medical Center (Charleston). Note: There is a 4th site involved in this study (Bedford) but we are not identifying and recruiting Veterans from this site. Veterans with, or at risk for, cardiovascular disease (CVD) who had at least 1 PC visit in the prior year, will be eligible for the study, to ensure that included Veterans are at least minimally engaged in VA care. We define CVD patients as those with International Classification of Disease 10 (ICD10) diagnoses indicating coronary artery disease, cerebrovascular disease, or peripheral artery disease, and patients with CVD risk factors as having diagnoses of hypertension, diabetes mellitus (DM), or hyperlipidemia. We will not exclude any patients based on gender, race, or other classes (e.g., disabilities). We will exclude patients with impaired decision-making capacity and who are illiterate or have limited or no English proficiency.

Among study participants, we will also recruit a purposeful sample of Veterans who participated in the trial as well as representatives of the VA and community programs to which participants are referred as a result of the trial. For the Veteran interviews, we will seek three Veteran types: Veterans who did not connect to new resources; Veterans who connected to new resources but did not have their unmet needs met, and Veterans who connected to new resources and had their needs met. For the VA and community program representatives, we will seek up to five of the most frequently used programs at each study site. We will not exclude any potential respondents for the qualitative interviews based on gender, race, or other classes (e.g., handicapped).

5.5 Study Evaluations

RCT participants will be asked to complete three brief surveys over a 6-month period. A small sub-set of participants will additionally be invited to participate in qualitative interviews.

Index Unmet Need Screen (survey #1): We will assess unmet needs among trial participants based on the index screen (administered prior to randomization). See **Appendix I** for the Index Unmet Need Survey.

Eight-Week Follow-Up Survey (survey #2): Eight weeks after the index screen, the RA will conduct phone follow-up with each Veteran to assess if they connected to any new resources in the intervening time and if so, to which one(s). See **Appendix J** for the Eight-Week Follow-Up Survey and accompanying phone script.

6-Month Unmet Need Re-Screen (survey #3): Six months after the index screen and by phone, the RA will re-administer the unmet need survey modified slightly

to exclude questions related to preferences for assistance (see **Appendix K** for the Six-Month Unmet Need Survey and accompanying phone script). We will define unmet need reduction in two ways: 1) one or more of baseline unmet needs no longer identified as an unmet need at the 6-month re-screen; and 2) percentage of baseline needs not reported as unmet needs at 6-month rescreen.

Qualitative Interviews with Veterans: Among study participants, we will purposefully select and recruit 60 Veterans to participate in qualitative interviews. The interviews are designed to understand the conditions that facilitate or impede a Veteran connecting to resources, as well as the conditions under which resources do or do not address a Veteran's needs. The RA at each study site will conduct the interviews. See **Appendix L and M** for the Veteran Interview Guides and accompanying phone scripts).

Qualitative Interviews with Representatives of VA and Community Resources: To understand how VA- and community-based programs experience the intervention, we will interview a purposeful sample of the VA- and community-based programs that trial participants used as a result of the intervention. The RA at each study site will conduct the interviews. See **Appendix N** for the Resource Representative Interview Guide and accompanying phone script.

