Appendix I: Index Unmet Needs Screening Tool

DEMOGRAPHICS

1. Please indicate which of following types of people currently live with you in your household (*check all that apply*)

- My spouse or partner
- My child(ren) under age 18
- My adult child(ren) age 18 or older
- My parent(s)
- Extended family
- Roommate(s) not related to me
- Other individuals

2. Overall, which one of the following best describes how well you are managing financially these days?

- Living comfortably
- Doing OK
- Just getting by
- Finding it difficult to get by

3. Are you of Hispanic or Latino origin or descent?

- Yes, Hispanic or Latino
- No, not Hispanic or Latino

4. What is your race? Please select all that apply.

- White
- Black or African-American
- Asian
- Native Hawaiian or other Pacific Islander
- American Indian or Alaska Native
- Other

5. What is your gender

- Man
- Woman
- Transgender man
- Transgender woman
- Non-binary
- Other

HOUSING AND UTILITIES

6. In the past 6 months, have you been living in stable housing that you own, rent, or stay in as part of a household?

- Yes
- No

7. Are you worried or concerned that in the next 2 months you may NOT have stable housing that you own, rent, or stay in as part of a household?

- Yes
- No

7a. (If Yes to Q6 or Q7): Are you already receiving assistance with your housing needs?

7b. (If Yes to 7a): Would you like additional assistance?

7c. (If No to 7a): Would you like assistance with your housing needs?

8. In the past 6 months has the electric, gas, oil or water company threatened to shut off service in your home?

- Yes
- No
- Already shut off
- Not applicable

8a. (If Yes/Already shut off): Are you already receiving assistance with your gas, oil or water company needs?

8b. (If Yes to 8a): Would you like additional assistance?

8c. (If No to 8a): Would you like assistance with your gas, oil or water company needs?

EMPLOYMENT AND FOOD

9. Are you currently:

- Employed for wages
- Self-employed
- Out of work for 1 year or more
- Out of work for less than 1 year
- A Homemaker
- A Student
- Retired
- Unable to work

9a. Do you want help finding or keeping work or a job (check all that apply)?

- Yes, help finding a job
- Yes, help keeping work
- I do not want or need help
- I am already receiving assistance with my employment needs

10. How often were the following statements true for you in the past 6 months?

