i. Within the past 6 months, you worried that your food would run out before you got money to buy more.

- Often true
- Sometimes true

- Never true

ii. Within the past 6 months, the food you bought just didn't last and you didn't have money to get more.

- Often true
- Sometimes true
- Never true

10a. (If Often/Sometimes true to 10i or 10ii): Are you already receiving assistance with your food needs?

10b. (If Yes to 10a): Would you like additional assistance?

10c. (If No to 10a): Would you like assistance with your food needs?

LEGAL AND TRANSPORTATION

11. Are you currently dealing with any legal issues, for which you may need assistance?

- Yes
- No

11a. (If Yes): Are you already receiving assistance with your legal needs?

11b. (If Yes to 11a): Would you like additional assistance?

11c. (If No to 11a): Would you like assistance with your legal needs?

12. In the past 6 months, has lack of transportation kept you from medical appointments, meetings, work, or getting things needed for daily living: *Check all that apply*

- Yes, it has kept me from medical appointments or from getting my medications
- Yes, it has kept me from non-medical meetings, appointments, or getting the things that I need
- No

12a. (If Yes): Are you already receiving assistance with your transportation needs?

12b. (If Yes to 12a): Would you like additional assistance?

12c. (If No to 12a): Would you like assistance with your transportation needs?

SOCIAL AND EMOTIONAL STATUS

13. In the last 6 months, how often did you feel lonely or isolated?

- Never
- Rarely
- Sometimes
- Often

- Always

13a. (If Sometimes/Often/Always): Are you already receiving assistance with your feelings of loneliness or isolation?

13b. (If Yes to 13a): Would you like additional assistance?

13c. (If No to 13a): Would you like assistance with your feelings of loneliness or isolation?

14. Stress is when someone feels tense, nervous, anxious, or can't sleep at night because their mind is troubled. In the last 6 months, how often did you feel stressed?

- Not at all
- A little bit
- Somewhat
- Quite a bit
- Very much

14a. (If Somewhat/Quite a bit/Very much): Are you already receiving assistance with your feelings of stress?

14b. (If Yes to 14a): Would you like additional assistance?

14c. (If No to 14a): Would you like assistance with your feelings of stress?

EXPOSURE TO VIOLENCE

15. Is anyone in your life hurting or threatening you?

- Yes
- No

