Appendix K: Six-Month Follow-Up Survey

Phone Contact:

Hello, my name is _____, I'm calling from the (Name of VAMC). I am trying to reach [Name of Veteran].

Not Present: I'll call back another time, thank you. Is there a good time to try calling back?

Voicemail: Hello, my name is [name of research team member], I am calling from the (Name of VAMC). I wanted to speak with [Name of Veteran] about the Resource Needs Study. It's time to complete one of the brief questionnaires that are part of this study, it will only take about 10 minutes to complete. Please contact me at [name]. If you get my voicemail please leave your name, the best number to reach you at, and the most convenient times to reach you. Thank you.

Present: Hello, my names is [name of research team member] and I work at the (Name of VAMC). I wanted to speak with you about the Resource Needs Study you are participating in. It's time to complete one of the brief questionnaires that are part of this study, it will only take about 10 minutes to complete. Do you have a few minutes now?

If No: When is a good time for you to answer some questions about your social circumstances? (*SCHEDULE A TIME AND CONFIRM BEST CONTACT NUMBER*)

If Yes: Great, let's get started.

Screening Survey

HOUSING AND UTILITIES

1. In the past 6 months, have you been living in stable housing that you own, rent, or stay in as part of a household?

- Yes
- No

2. Are you worried or concerned that in the next 2 months you may NOT have stable housing that you own, rent, or stay in as part of a household?

- Yes
- No

3. In the past 6 months has the electric, gas, oil or water company threatened to shut off service in your home?

- Yes
- No
- Already shut off
- Not applicable

EMPLOYMENT AND FOOD

4. Are you currently:

- Employed for wages
- Self-employed
- Out of work for 1 year or more
- Out of work for less than 1 year
- A Homemaker
- A Student
- Retired
- Unable to work

5. How often were the following statements true for you in the past 6 months?

i. Within the past 6 months, you worried that your food would run out before you got money to buy more.

- Often true
- Sometimes true
- Never true

ii. Within the past 6 months, the food you bought just didn't last and you didn't have money to get more.

- Often true
- Sometimes true
- Never true

LEGAL AND TRANSPORTATION

6. Are you currently dealing with any legal issues, for which you may need assistance?

- Yes
- No

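### The 6-month re-screen drops item 9a, so an employment need as asked at index cannot be re-measured, and the literal reduction definitions would score it as resolved

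*Combined protocol and SAP*

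**What the plan says.** Employment is one of the nine needs (Section 3.0, Aim 1), and one reported need is enough for randomization (Section 5.2, Step 3).

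In Appendix I, employment starts with a status list, "9. Are you currently", whose options run from employed to retired and unable to work. No option is marked as a need. The next item, "9a. Do you want help finding or keeping work or a job (check all that apply", has no skip condition. Its options are help finding a job, help keeping work, "I do not want or need help", and a statement that employment help is already being received.

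Section 5.5 has the survey repeated at six months, changed "to exclude questions related to preferences for assistance". In Appendix K the status list returns as "4. Are you currently", and the next item is food: "5. How often were the following statements true for you in the past 6 months". Nothing corresponds to 9a.

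Section 5.5 defines reduction in two ways: "one or more of baseline unmet needs no longer identified as an unmet need at the 6-month re-screen", and the percentage of baseline needs not reported at re-screen. Section 5.6 analyses change from baseline in the proportion of unmet needs in an expected 220 re-screened Veterans.

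**The concern.** Elsewhere in the index screen a parent item establishes the need and the lettered items ask about assistance. Food is typical: "10a. (If Often/Sometimes true to 10i or 10ii): Are you already receiving assistance with your food needs". Dropping the lettered items there costs nothing. In employment the lettered item carries the need, so the same editing rule removes the measurement.

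An employed Veteran who asks at index for help keeping work, or a retired Veteran who wants a job, has no item at six months on which to report that need again. Both reduction definitions turn on a need being absent at re-screen, and a need that is never asked about is always absent. Unmet need reduction is the first secondary outcome listed under Aim 2 and a mediator in the conceptual path of Section 5.6. Aim 1 prevalence and Aim 2 reduction could also end up using different definitions of one of the nine needs.

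**Working it through.** **Comparison of the two surveys**

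| Need | Index item (Appendix I) | 6-month item (Appendix K) |
|---|---|---|
| Housing | 6, 7 | 1, 2 |
| Utilities | 8 | 3 |
| Employment | 9 (status), 9a (need) | 4 (status only) |
| Food | 10 i, ii | 5 i, ii |
| Legal | 11 | 6 |
| Transportation | 12 | 7 |
| Isolation | 13 | 8 |
| Stress | 14 | 9 |
| Safety | 15 | 10 |

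Appendix K is numbered 1 to 10 without a gap, so the omission is not a lost line. Eight needs keep their need item; employment does not.

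**Plan's own figures (context, not disputed).** The re-screen sample is 880 × 0.5 × 0.5 = 220. With ICC .01 over three sites the design effect is 1 + (220/3 − 1) × 0.01 = 1.723, and 220/1.723 = 127.7. At f² = .09, noncentral-F power is 86% with 2 numerator df and 81% with 3, in line with the stated 80%. The plan gives no figure for employment need.

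**Definition 1, literal scoring.** Let e be the share of re-screened Veterans with a 9a-based need, all scored as reduced, and p the true proportion reduced in an arm. If p is the same with and without an employment need, the observed proportion is e + (1 − e)p, and the arm difference is multiplied by (1 − e). Assumed: p = 40% v 55%.

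| e | Observed | Difference (points) | OR |
|---|---|---|---|
| 0 | 40.0% v 55.0% | 15.0 | 1.83 |
| 10% | 46.0% v 59.5% | 13.5 | 1.72 |
| 20% | 52.0% v 64.0% | 12.0 | 1.64 |
| 30% | 58.0% v 68.5% | 10.5 | 1.57 |

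The loss is the fraction e of the difference, not e percentage points.

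A second illustration uses the plan's detectable OR of 2.94 with an assumed 30% in the lower arm (30% v 55.8%). It is a pairwise comparison with 220/3 ≈ 73 per arm, two-sided 5%, normal approximation, no ICC adjustment. OR and power are 2.94 and 89% at e = 0, 2.57 and 81% at 10%, 2.32 and 71% at 20%, and 2.14 and 61% at 30%.

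**Definition 2, literal scoring.** A Veteran with k baseline needs, one of them employment, is credited with 1/k automatically: 100% if k = 1, 50% if k = 2, 25% if k = 4. If each other need resolves at rate r, the expected score is 1/k + (1 − 1/k)r, so the arm difference overall is multiplied by (1 − e/k). For r = 40% v 55% and e = 20%, the 15 points become 12.0 (k = 1), 13.5 (k = 2) or 14.25 (k = 4).

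**The case against.** The strongest reply is that 9a is worded as a preference question, close to the items asking whether assistance is wanted, so the team may regard status as the employment screen. Appendix K keeps the status list, and status scored identically at both screens would yield a measurable change. This limits the point to the need as asked at index. It does not remove it. No section available states a status rule. Such a rule would miss the employed Veteran who wants help keeping work and the retired Veteran who wants a job, and would count an out-of-work Veteran who wants no help. The part of the Appendix G script just before randomization was not in the text available for this review, so a scoring instruction could sit there. That would settle the index rule but would not put 9a into Appendix K.

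A reader might go further and infer that the trial will score every employment need as resolved. The documents do not say so. They are silent on a need that is not re-asked, and the first definition can be read as presupposing that the need was assessed again. Automatic resolution follows only from the literal reading.

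Two further replies stand. The scoring would apply alike in all arms and would work against finding an effect, since more false successes fall where true reduction is lower. The scope is one need of nine, in a secondary outcome and the exploratory mediation analyses. The primary outcome, connection to new resources at eight weeks, does not use the re-screen.

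**Conclusion.** The omission is a matter of text and is certain: an employment need affirmed on 9a cannot be re-measured with Appendix K. The bias is conditional. If the definitions are applied literally, reduction is inflated in every arm and arm differences are diluted, by the fraction e under definition 1 and by e/k under definition 2. The sizes rest on assumed reduction rates, an assumed e, and equal reduction with and without an employment need. At e = 10% the effect is modest (OR 1.83 to 1.72); at 30% it is material for a sample of 220. The wider claims, that employment change is unmeasurable on any definition or that resolution will certainly be credited, are not supported. The correction is cheap and worth making.

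**What to change.** Put item 9a back into Appendix K directly after item 4, word for word, and exempt it from the exclusion in Section 5.5.

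State one employment-need rule for both screens. Under it, ticking only that employment help is already being received must not count as resolution, just as receiving assistance does not cancel a need in the other domains. Otherwise a Veteran connected to a job program and still without adequate work would be scored as resolved. Connecting Veterans to services is what the Assistance arm does, so that error could favor it.

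For Veterans already re-screened without 9a, treat 6-month employment need as missing and leave it out of the numerator and denominator of both reduction measures. Report the number affected by arm.

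The cost is one question on a call announced as about 10 minutes, a minor survey amendment and a line or two of scoring text. Employment is not evaluable for Veterans already re-screened, and those whose only baseline need was employment then have no evaluable need and drop out of both measures.

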3.0 Objectives

We will compare outcomes among Veterans with or at risk for CVD at three VA sites randomized (at the site-level) to one of three arms: 1) unmet needs screening only, 2) screening + provision of tailored resource sheets to address identified unmet needs, or 3) screening + tailored resource sheet + social worker support. We will quantitatively examine associations of unmet needs with baseline and follow up outcomes, assessing the impact of varying intensity referral approaches. We will also qualitatively examine stakeholder perspectives about the barriers and facilitators to identifying and addressing unmet needs to provide insight into the relative success of each study arm. Specific aims are:

Aim 1: Describe the prevalence and distribution of nine unmet needs (housing, food insecurity, utility insecurity, transportation, legal needs, employment, safety, social isolation, stress), and identify their associations with baseline sociodemographic characteristics, adherence, utilization and clinical outcomes.

Aim 2: Compare the effectiveness of varying intensity referral strategies to address unmet needs on the primary outcome of connection to new resources to address unmet needs, and on secondary outcomes of post-intervention change in unmet needs, adherence, utilization, and clinical outcomes. **H1.** Based on Maslow's model, we hypothesize that referrals (and more so for those enhanced by SW support) will increase the likelihood of patients connecting to new resources to address unmet needs (primary outcome), which may then have positive sequential effects, with reduced unmet needs, increased adherence, decreased urgent care/preventable utilization, and ultimately, improved clinical outcomes.

Aim 3: Identify barriers and facilitators to Veterans' connecting with resources to address unmet needs and getting needs met, and explore potential explanatory factors related to the relative success of each study arm.

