5.6 Data Analysis

Study Sample and Power Analysis

We aim for a total of 880 Veterans enrolled in the RCT (293/arm) based on power analyses provided below. Based on the study team's prior primary care-based studies with a similar recruitment approach, we anticipate 80% of patients approached to complete the index screen will participate. Based on pilot data from the Bedford MA VA where 78% of Veterans reported one or more needs, we then conservatively estimate that 50% of Veterans screened will report at least one of the nine unmet needs for which we will screen.

Thus, to yield a final sample of 880 Veterans with at least one unmet need enrolled in the study, we anticipate needing to approach 2200 eligible Veterans (733/site, or ~3 patients/day/site) i.e., of 2200, 80% (1760) will agree to participate in the study and of these, 50% (880) will have one or more unmet needs and be eligible for the RCT. If the participation rate or proportion of Veterans reporting at least one unmet need is lower than expected, we will increase the number of Veterans that we approach. We reviewed VA administrative data to determine the anticipated weekly count of Veterans eligible per site to participate in the study and there are more

than enough eligible Veterans to approach for additional screening if needed. We also anticipate drop-out rates at the 8-week follow-up survey to assess connection to resources and the 6-month unmet needs re-screen, respectively. Though the study team's prior study achieved a 65% follow up participation rate, here we conservatively anticipate a 50% participation rate for both the 8-week follow-up survey and the 6-month re-screen, reducing the sample for the three arms first to 440 Veterans total and then to 220 Veterans total.

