Unmet Need Reduction: Similar analyses will be used to examine differences across our three study arms in change from baseline in the proportion of unmet needs among the sub-sample of participants who complete the re-screening at 6-months post-referral. Among this sub-sample (N=220, assuming attrition rates of 50% at both the 8-week and 6-month follow-up phone surveys), we will have 80% power to detect a small-to-medium effect ($f^2=.09$; OR=2.94) across the three arms in terms of unmet need reduction using 2-tailed significance tests at the $\alpha=.05$ level, even if we assume a conservative ICC value for patients nested within sites of .01.

Differences in Intervention Effectiveness. In addition to examining how the S&R influences connection to new resources, we will conduct additional analyses to examine whether there is differential impact between the two referral arms (Awareness and Assistance) on connection to new unmet needs resources; unmet need reduction; and adherence, utilization and clinical outcomes among Veterans with certain unmet needs or with fewer unmet needs. While we predict that providing SW support (Assistance arm) will generally have a larger impact on outcomes than providing a Resource Sheet alone (Awareness arm), it would be beneficial to know if the Resource Sheet alone (or even the screening and

provision of generic list of resources) is sufficient to produce comparable changes in outcomes among Veterans with certain unmet needs or among Veterans with fewer unmet needs. If true, future implementation research could create tailored interventions that funnel the resources for more time- and cost-intensive referral strategies to only those Veterans who need it most.

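### Unmet need reduction counts only resolved index needs in 5.5, while 5.6 analyses a change in proportion with no denominator; the two must be reconciled and new needs reported

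*Combined protocol and SAP*

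**What the plan says.** Aim 2 (section 3.0) lists "secondary outcomes of post-intervention change in unmet needs".

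Section 5.5, under the six-month re-screen, states: "We will define unmet need reduction in two ways". The first is binary: "one or more of baseline unmet needs no longer identified as an unmet need at the 6-month re-screen". The second is a "percentage of baseline needs not reported as unmet needs at 6-month rescreen". Both look only at needs present at the index screen.

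Section 5.6, under Unmet Need Reduction, holds the only analysis text and the only power statement for this outcome. It examines "differences across our three study arms in change from baseline in the proportion of unmet needs" among those re-screened at six months. It gives no denominator for the proportion and does not refer back to 5.5. The power statement is 80% power for f²=.09 or OR=2.94, with N=220, two-tailed α=.05 and ICC=.01.

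New needs are collected. Section 5.5 says that "the RA will re-administer the unmet need survey modified slightly", the modification being removal of the questions on preference for assistance. Appendix K repeats the need domains but leaves out item 9a of Appendix I, which asks whether the Veteran wants help finding or keeping work.

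**The concern.** Aim 2 asks about change in needs. A measure built only from index needs cannot register a need that appears later, so a Veteran who is worse off overall can be reported as reduced. The binary version also becomes easier to meet as the number of index needs rises. That matters because 5.6 plans to compare effects among Veterans with fewer needs.

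The mismatch between 5.5 and 5.6 adds a second problem. There are two definitions in one section, a differently worded outcome in the other, one power statement and no named main definition. The outcome also feeds the analyses of differential effectiveness and the mediation analyses in 5.6, so the ambiguity carries forward.

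**Working it through.** **1. The plan's power figure.** Inputs are from 5.6: 880 randomised, 50% retained at each follow-up, three sites, ICC .01, α .05 two-tailed.
- Retained N = 880 × 0.5 × 0.5 = 220.
- Design effect = 1 + (220/3 − 1) × .01 = 1.723. Effective N = 220/1.723 = 127.7.
- Noncentral F test with noncentrality f² × 127.7, and OR = exp(2f × π/√3).
- With 3 numerator df, power at f²=.09 is 0.809 and the detectable f² is 0.088, which gives OR 2.94. This matches. With 2 df, power is 0.860 and the detectable OR is 2.74. The plan does not state the df; 3 is inferred from the match.

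The figure reproduces. What is missing is the outcome to which it belongs.

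**2. Scoring example Veterans.** The last column assumes that the 5.6 proportion is out of nine needs.

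| Veteran | Index needs | Resolved | New | Six-month needs | Any resolved | % resolved | Change, of nine |
|---|---|---|---|---|---|---|---|
| A | 2 | 1 | 3 | 4 | yes | 50% | +2/9 |
| B | 1 | 1 | 2 | 2 | yes | 100% | +1/9 |
| C | 4 | 1 | 0 | 3 | yes | 25% | −1/9 |

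A and B have more needs than at index but count as reduced on both 5.5 definitions. On percentage resolved, B (worse off) scores better than C (better off).

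**3. What the 5.6 denominator changes.** Take Veteran A.
- Out of nine needs: 2/9 at index, 4/9 at six months, change +2/9.
- Out of index needs, counting only those needs: 2/2 = 100% at index, 1/2 = 50% at six months, change −50 points. This is percentage resolved with the sign reversed. Every Veteran would start at 100%, which makes change from baseline an odd description.

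The two readings give opposite signs for the same Veteran.

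**4. Dependence on the index number.** If each need resolves with probability q, the chance of any resolved with k index needs is 1 − (1 − q)^k. At an assumed q = 0.30 this is 0.30, 0.51, 0.66 and 0.76 for k = 1, 2, 3 and 4.

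**5. How often (all rates assumed).** Domains are taken as independent.
- One to four index needs, resolution 0.2 to 0.4, new onset 0.05 to 0.15 per other domain: about 1% to 15% of Veterans meet any-resolved while having more needs than at index. Of those meeting any-resolved, about 10% to 73% have no net fall.
- Mean 2.2 index needs, resolution 0.4, onset 0.1: 63% meet any-resolved and 40% have a net fall. Of the 63%, 37% have no net fall and 10% have more needs.

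**6. What a net count costs or gains (all rates assumed).** Two arms of 73 (220/3), no clustering, linear models, intervention raising resolution of index needs by 0.15 and leaving onset alone.
- Mean 2.2, resolution .40 against .55, onset .10: power is about 65% to 67% for percentage resolved, 44% to 46% for the six-month number adjusted for the index number, and 35% to 37% for raw change in number.
- Mean 2.6, resolution .50 against .65, onset .05: adjusting in place of raw change raises power from 48% to 67%.

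**The case against.** **Index needs are what the intervention targets.** Appendix A says that Resource Sheets are tailored to needs found at the index screen, and the eight-week survey (Appendix J) asks about help with those needs. Resolution of them is a legitimate effect measure. This stands: the 5.5 definitions should be kept, and net burden is a different question, not a correction.

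**A net count may lose power.** If the intervention acts only on index needs, new onsets are noise, as step 6 shows. This also stands, so the net count should not be imposed as the lead measure.

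**The 5.6 wording may not be a third outcome.** A reader might infer that 5.6 counts new needs and that three outcomes share one name. The text does not support that: with index needs as denominator, 5.6 is the percentage measure with its sign changed. The missing denominator is the defect.

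**The definitions may be ranked elsewhere.** Section 5.1 (Safety and Data Monitoring Plan) mentions a Data Analysis Plan submitted for DSMB approval. It was not available for this review and may name a main definition. Even so, 5.5 and 5.6 should agree with each other.

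**Bias between arms.** A reader might infer that social worker assessment uncovers more needs in the Assistance arm and distorts the comparison. Appendix A speaks of uncovering details of needs, and the re-screen is a fixed telephone survey given to all arms, so this is not established. Were it true, it would affect a net count and not the 5.5 definitions.

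**Conclusion.** The point holds in limited form. It follows from the text and needs no simulation: both 5.5 definitions ignore new needs, so a Veteran with more needs can count as reduced, and 5.6 analyses a differently worded quantity whose denominator is missing. Neither section names a main definition.

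Its weight is moderate. This is one secondary outcome; connection to new resources at eight weeks is untouched, and the power figure is arithmetically sound.

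The percentages in steps 5 and 6 rest wholly on assumed resolution and onset rates and on independent domains. A reader might take the high any-resolved rate without intervention as evidence of a biased comparison. It is not: chance resolution occurs in every randomised arm. It affects how an improvement rate should be read, not which arm is favoured.

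**What to change.** Before outcome data are examined, amend the wording of 5.5 and 5.6:

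- State the denominator of the 5.6 proportion and how a need first reported at six months counts.
- Name one main definition. Whether resolution or net count leads is the sponsor's choice: the net count captures new needs, but may have less power if the intervention acts only on index needs.
- Keep both resolution measures. Report beside them the number of needs at six months, analysed with adjustment for the index number and not as raw change.
- Adjust the any-resolved analysis for the index number too, because it rises mechanically with that number.
- Score employment the same way at both screens, for example from items asked at both. If it were scored from item 9a at index, Appendix K could not record it again, and an employment need would drop out by construction. That would affect the 5.5 definitions as well as a net count.
- Tie the f²=.09/OR=2.94 statement to the named outcome. It need not be recalculated.

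The cost is wording and one added analysis of data already planned for collection. The reported picture of improvement may be less favourable once new needs are shown.
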